APPENDIX L SUMMARY OF CHANGES

Study CFZ014 was amended to include the following:

- Adverse events of pulmonary hypertension and TTP/HUS were added to the dose modification guidelines to be consistent with the guidance provided in the updated Investigator Brochure version 15, dated 26February 2015.
- Updated PK timepoints for intensive and sparse PK sampling as carfilzomib will be administered as an IV infusion over 30 minutes in the once-weekly arm and over 10 minutes in the twice-weekly arm. There is a mid-infusion PK timepoint (15 min after the start of infusion) that is only applicable for the carfilzomib once weekly arm, where carfilzomib is administered over 30 min. The protocol has been amended to state that this PK timepoint, 15 min after the start of infusion, is only required for the carfilzomib once weekly arm.
- Updated clinical information for carfilzomib to be consistent with IB Version 15.0.
- Updated text in the safety section of the protocol to accurately reflect Drug Safety requirements and how and to whom information is provided.
- Updated Medical Monitor information.

In addition, administrative updates have been made to enhance document clarity.

Changes made to this protocol are listed in the table below.

APPENDIX L SUMMARY OF CHANGES

Amendment 1.0:

Study CFZ014 was amended to include the following:

- Clarified that consent is required from subjects if additional blood samples will be collected for PK (sparse sampling) and for the intensive PK and PDn substudy.
- Clarified that dexamethasone should be administered orally on Day 22 in Cycles 1–9.
- Clarified that dexamethasone will not be administered on Day 22 after Cycle 9.
- Clarified that events occurring prior to consent should be captured as medical history information.
- Clarified the timing of safety labs after Cycle 4.
- Clarified the timing of patient reported outcome questionnaires.

In addition, administrative updates have been made to enhance document clarity. Changes made to this protocol are listed in the table below.

Amendment 1.1:

Two additional administrative updates were made to correct errors found in Protocol CFZ 014 Amendment 1.0:

- The header on pages 100-109, Appendix F, of protocol CFZ014 read “Protocol 2011–003, Amendment 3” instead of reading as “Clinical Study Protocol No. CFZ014”.
- Two hyperlinks in the footnote of Appendix A read “Error! Reference source not found” instead of linking to Sections 10.4.1 (Hematology) and 10.4.2 (Serum Chemistry), respectively.

Appendix A.	Handling of Dates, Incomplete Dates and Missing Dates for Adverse Events and Concomitant Medications1	40
Appendix B.	Reference Values/Toxicity Grades2	41
Appendix C.	Patient-reported Outcome Forms/Instruments3	43

Statistical Analysis Plan: 20140355

Date: 09 Jun 2017 Page 5

Table of Abbreviations

Term or Abbreviation	Description
AE(s)	Adverse Event(s)
ANC	Absolute Neutrophil Count
AUC	Area Under Curve
BSA	Body Surface Area
CBR	Clinical Benefit Rate
CDM	Clinical Data Management
CI	Confidence Interval
Cmax	Maximum plasma concentration
CR	Complete Response
CrCl	Creatinine Clearance
CSR	Clinical study report
CT-L	chymotrypsin-like
CV	coefficient of variation
BSA	Body Surface Area
CRF	Case Report Form
DMC	Data Monitoring Committee
DCB	Duration of Clinical Benefit
DOR	Duration of Response
EBMT	European Group for Blood and Marrow Transplant
ECG	Electrocardiogram
ECOG	Eastern Cooperative Oncology Group
ELISA	Enzyme-linked Immunosorbent Assay
EORTC	European Organization for Research and Treatment of Cancer
EuroQOL	European Quality of Life
EQ-5D-5L	European Quality of Life-5 Dimensions
EOI	Event of Interest
EOT	End of Treatment
E-R	Exposure-Response
FDA	Food and Drug Administration
FISH	Fluorescence in situ hybridization
GSO-DM	Global Study Operations-Data Management
HR	Hazard Ratio
IBG	Independent Biostatistics Group

Statistical Analysis Plan: 20140355

Date: 09 Jun 2017 Page 6

IMiD Immunomodulatory Agent

IMWG-URC International Myeloma Working Group-Uniform Response Criteria

IPD Important Protocol Deviation
IRC Independent Review Committee
ISS International Staging System

IV Intravenous(Iy)
KM Kaplan-Meier

LC–MS/MS Liquid chromatography–mass spectrometry/ mass spectrometry

LFT Liver Function Test

LVEF Left Ventricular Ejection Fraction

MedDRA Medical Dictionary for Regulatory Activities

MR Minimal Response

NCI-CTCAE National Cancer Institute-Common Terminology Criteria for

Adverse Events

ORR Overall Response Rate

OS Overall Survival

PASS Power Analysis and Sample Size Software

PD Progressive Disease
PDn Pharmacodynamics

PFS Progression-free Survival

PI Proteasome Inhibitor
PK Pharmacokinetics

PKDM Pharmacokinetics and Drug Metabolism

PO Orally

PR Partial Response

QLQ-C30 Quality of Life Core Module

QLQ MY20 Quality of Life Multiple Myeloma Module 20

QTc corrected QT-interval

RDI Relative Dose Intensity

SAE(s) Serious Adverse Event(s)

SAP Statistical Analysis Plan

sCR Stringent Complete Response

SD Stable Disease

SSAP Supplemental Statistical Analysis Plan

VGPR Very Good Partial Response

WHODRUG World Health Organization Drug dictionary

Statistical Analysis Plan: 20140355

Date: 09 Jun 2017 Page 7

1. Introduction

The purpose of this Statistical Analysis Plan (SAP) is to provide details of the statistical analyses that have been outlined within the protocol for carfilzomib study 20140355, dated 08 Feb 2017. The scope of this plan includes the interim analysis and the final analysis that are planned and will be executed by the Biostatistics department unless otherwise specified. PK analyses will be provided by the Department of Clinical Pharmacology, Modeling & Simulation (CPMS).

2. Objectives

2.1 Primary Objective

The primary objective of this study is to compare the progression-free survival (PFS) of once weekly carfilzomib dosing in combination with dexamethasone to the PFS of twice weekly carfilzomib dosing in combination with dexamethasone in subjects with relapsed and refractory multiple myeloma who have received prior treatment with a proteasome inhibitor and an IMiD (immunomodulatory agent).

2.2 Secondary Objectives

The secondary objectives of the study are to compare the following between treatment groups:

- Overall response rate (ORR)
- Overall survival (OS)
- Safety and tolerability
- Pharmacokinetics (PK) of carfilzomib using sparse sampling

2.3 Exploratory Objectives

The exploratory objectives are to evaluate the following between treatment groups:

- Intensive pharmacokinetics (PK) and pharmacodynamics (PDn) of carfilzomib in a subset of subjects (substudy)
- All subscales of the European Organization for Research and Treatment of Cancer (EORTC) Quality of Life Core Module (QLQ-C30), and the EORTC Quality of Life Multiple Myeloma Module 20 (QLQ-MY20)
- European Quality of Life-5 Dimensions (EQ-5D-5L); a standardized measure of health status developed by the European Quality of Life (EuroQol) Group
- Patient reported convenience and satisfaction with the carfilzomib dosing schedule

Statistical Analysis Plan: 20140355

Date: 09 Jun 2017 Page 8

Healthcare resource utilization

3. Study Overview

3.1 Study Design

This is an open label, multicenter, randomized Phase 3 study comparing once weekly carfilzomib dosing in combination with dexamethasone to twice weekly carfilzomib dosing in combination with dexamethasone in subjects with relapsed and refractory multiple myeloma, 2 or 3 prior therapies, and previously treated with a proteasome inhibitor and an IMiD. The primary endpoint is PFS. The study design is illustrated in Figure 1.

Eligible subjects will be randomized in a 1:1 ratio to receive a regimen consisting of either once-weekly or twice weekly carfilzomib in combination with dexamethasone.

The randomization will be stratified by:

- International Staging System (ISS) Stage at study entry (Stage 1 versus Stage 2 or 3) per International Myeloma Working Group (Greipp 2005).
- Refractory to bortezomib treatment (Yes versus No)
- Age (< 65 versus ≥ 65 years)

Study treatment will be administered in 28 day cycles. Subjects will receive the study treatment determined by randomization until disease progression, unacceptable toxicity, withdrawal of consent, or death (whichever occurs first). No crossover between the 2 treatment groups will be allowed.

Following termination of study treatment, all subjects will be followed for disease status (if progressive disease [PD] has not been reached), subsequent antimyeloma treatment, and survival.

[figure not shown]
All subjects will be followed for safety for at least 30 additional days after the last study treatment administration. All treatment-related adverse events (AEs) and serious adverse events (SAEs) will be followed until resolution or stabilization.

Statistical Analysis Plan: 20140355

Date: 09 Jun 2017 Page 9

Figure 1 Study 20140355 Schema

ECOG = Eastern Cooperative Oncology Group; IMiD = immunomodulatory agents; IV = intravenous(Iy); ORR = overall response rate; OS = overall survival; PD = disease progression; PFS = progression-free survival; PI = proteasome inhibitor; PO = orally.

Subjects will be assessed for response using central laboratory results every 28 days (\pm 4 days until confirmed PD. Long-term follow-up (LTFU) for disease status (only in cases where subjects discontinued treatment prior to PD) and for survival (after reaching PD) will continue after treatment discontinuation or until the subject has withdrawn consent for further participation, is lost to follow-up, has died, or the sponsor makes a decision to close the study. For subjects who discontinued treatment before disease progression occurred (such as for an adverse event, noncompliance, etc.), disease response assessments will be performed using central laboratory results every 28 ± 4 days until disease progression. Follow up for survival will continue approximately every 12 weeks \pm 28 days, or as needed, for all surviving subjects until study closure. For any subject who is lost to follow-up, the study site will attempt to ascertain survival information via public database search.

3.2 Sample Size

CC

Statistical Analysis Plan: 20140355

Date: 09 Jun 2017 Page 10

a total of 350 PFS events will be needed for the final PFS analysis, in order to have 83% power to detect a significant difference in PFS between the two treatment groups at 1-sided significance level of 0.025 with 1 interim analysis performed at approximately 75% information time (i.e., 75% of 350 PFS events) using the Lan-DeMets spending function with an O'Brien-Fleming approach, CCI

There is no target number of events for OS analysis. The analysis of OS will be conducted at the time of the PFS analysis (interim or final), only if both PFS and ORR analyses are positive.

4. Study Endpoints and Covariates

4.1 Study Endpoints

Primary Endpoint

The primary endpoint is PFS, which is defined as the time in months from randomization to the earlier of disease progression or death due to any cause.

Secondary Endpoints

The secondary endpoints of the study are as follows:

- ORR, defined as the proportion of subjects who achieved a confirmed PR, VGPR, CR, or sCR, according to the IMWG URC
- OS, defined as the time in months from randomization to death due to any cause
- Safety and tolerability
- Sparse PK

Statistical Analysis Plan: 20140355

Date: 09 Jun 2017 Page 11

4.2 Planned Covariates

The primary analysis of PFS, ORR and OS will be stratified by the stratification factors at randomization: ISS stage at study entry (Stage 1 versus Stage 2 or 3), refractory to bortezomib treatment (yes versus no), and age ($< 65 \text{ versus} \ge 65 \text{ years}$).

5. Hypotheses and/or Estimations

The inferential comparison of PFS between treatment groups will be made using a log-rank test stratified by randomization stratification variables. The 1-sided p-value from the stratified log-rank test will be compared against the value specified by the alpha spending function specified in Section 8 at the given analysis (interim or final) to test the null hypothesis that weekly arm doesn't have superior PFS than twice weekly arm. The inferential comparison of ORR between treatment groups will be made using a Cochran-Mantel-Haenszel test stratified by randomization stratification variables. The inferential comparison of OS between treatment groups will be made using a log-rank test stratified by randomization stratification variables.

6. Definitions

Anti-myeloma therapies during long term follow-up

Anti-myeloma therapies during long term follow-up will be those therapies entered in the anti-myeloma therapy case report form (CRF) administered during the long term follow-up period of the study.

Baseline

For analyzing progression-free survival time (PFS) and overall survival time (OS), baseline will be defined as the day of randomization.

For the analysis of other endpoints, baseline will be defined as the value measured on day1 of the first cycle of protocol-specified therapy. The protocol specifies that all study procedures on day 1 should be completed before the initiation of protocol-specified therapy, which will be the assumption in the analysis, unless the time of the assessment is recorded. If a day 1 value is not available, the latest value before the day of the start of protocol-specified therapy will be used. If a subject doesn't receive any protocol-specified therapy, then the latest value prior to or on randomization date will be used.

Best overall response

Statistical Analysis Plan: 20140355

Date: 09 Jun 2017 Page 12

Best overall response will be assessed by computational assessment, Independent Review Committee (IRC) and investigator. The primary analysis of ORR will be based on best overall response assessed by computational assessment.

Best overall response by computational assessment

Best overall response will be derived using a computer based algorithm for multiple myeloma disease assessments based on The International Myeloma Working Group Uniform Response Criteria (Durie et al. 2006, with corrections, Rajkumar et al. 2011) (IMWG-URC), the protocol, and The European Group for Blood and Marrow Transplant (EBMT) criteria (Bladé et al. 1998) for the assessment of minimal response only. The detailed algorithm is documented in a separated document 'SPECIFICATIONS FOR ONYX RESPONSE COMPUTATIONAL ASSESSMENT (ORCA) BASED ON IMWG UNIFORM RESPONSE CRITERIA'.

Best overall response by IRC assessment

Best overall response by IRC will be collected on CRF.

Best overall response by investigator assessment

Best overall response by investigator assessment is the best confirmed response by the analysis trigger date based on the responses by visit collected on myeloma response assessment eCRF. The response assessments done after initiation of new anti-myeloma therapy will be excluded from the analysis.

A confirmed response of minimal response (MR) or better requires at least two consecutive assessments with the same response or better. Stable disease (SD) requires a duration of at least 6 weeks. Progressive disease (PD) requires two consecutive PD assessments based on the same analyte except when PD is due to any of the following criteria:

- Definite development of new bone lesions or definite increase in the size of existing bone lesions
- Definite increase or new appearance of soft tissue plasmacytomas
- Definite increase of % plasma cells in Bone Marrow.

Best overall response will be decided in the following order of confirmed responses: stringent complete response (sCR), complete response (CR), very good partial response (VGPR), partial response (PR), MR, SD, PD starting from the best to the worst.

Statistical Analysis Plan: 20140355

Date: 09 Jun 2017 Page 13

Clinical Benefit Rate (CBR)

CBR is the proportion of subjects whose best overall response is MR, PR, VGPR, CR, or sCR.

Cumulative Dose of Study Treatment

Carfilzomib: Cumulative dose will be calculated in mg and mg/m². The cumulative dose in mg will be calculated as the summation of total quantity administered (mg) over all infusions. The cumulative dose in mg/m² will be calculated as the following over infusions.

$$\sum \frac{Total\ quantity\ administered\ (mg)}{BSA\ (m^2)}$$

BSA is to be determined by a standard formula, such as the Mosteller Formula (Mosteller 1987): body surface area (BSA) (m²) = ([Height (cm) × Weight (kg)]/3600)½. The one collected on cycle 1 day 1 will be used in the calculation till when BSA changes ≥20% from cycle 1 day 1. Every time BSA changes ≥20% from current BSA used in the calculation, the new BSA will be used for subsequent infusions. If BSA is >2.2, then 2.2 will be used in the calculation.

Dexamethasone: The cumulative dose in mg will be calculated as the summation of total quantity administered (mg) over the study.

Death Date

For subjects who die during the study, the death date will be recorded on the end of study CRF in the end of study date field. Incomplete death dates where only the day of death date is missing will be imputed using the following rules:

Day 1 of the month will be used if year and month indicate that death happened in different month from last known alive date;

One day after last known alive date will be used if death happened in the same month as last known alive date.

The imputed death date will be used in calculation of duration of response, progressionfree survival and overall survival.

Duration of Clinical Benefit (DCB)

Statistical Analysis Plan: 20140355

Date: 09 Jun 2017 Page 14

DCB will be calculated only for subjects who achieve a best overall response of MR or better, i.e., sCR, CR, VGPR, PR, or MR. The duration will be calculated in months from the earliest date a response of MR or better is first achieved and subsequently confirmed to the earliest date of confirmed PD or death due to any cause:

DCB=(PD/death date-MR/better response start date +1)/30.4

Subjects will be censored using the same censoring rules for PFS as listed in table 1 if applicable.

Duration of Response (DOR)

DOR will be calculated only for subjects who achieve a best overall response of PR or better, i.e., sCR, CR, VGPR, or PR. The duration will be calculated in months from the earliest date a response of PR or better is first achieved and subsequently confirmed to the earliest date of confirmed PD or death due to any cause:

DOR=(PD/death date-response start date +1)/30.4

Subjects will be censored using the same censoring rules for PFS as listed in table 1 if applicable.

Duration of Study Treatment

Duration of treatment with carfilzomib and dexamethasone will be defined as the time from the first start date of each drug to the last stop date of the drug. Duration of the whole study treatment will be from the earliest start date among the two drugs to the latest stop date among the two drugs.

End of Study Treatment Date

The end of study treatment date is the date the decision was made to end investigational product reported on the end of investigational product administration CRF.

End of Study

For an individual subject: a subject ends the study in the event of death, , consent withdrawal, or lost to follow-up. The end of study date will be captured on the end of study CRF.

For the study as a whole: the end of study as a whole is defined as the time when the last subject is assessed or receives intervention for the purposes of final collection of data for the final analysis of PFS, which will be triggered when 350 PFS events (PD or death) are reported or by end of year 2018, whichever is earlier. Subjects who have not

Statistical Analysis Plan: 20140355

Date: 09 Jun 2017 Page 15

completed all expected treatment at the time of the end of study as a whole will continue to follow protocol specified treatment and procedures until completion.

Enrollment Date

The date of enrollment is the date the subject gets randomized.

Fluorescent in Situ Hybridization (FISH) Risk Group

The subjects with genetic abnormalities t(4;14), t(14;16), and deletion 17p, as indicated on FISH/Conventional Cytogenetics CRF are categorized in the high risk group. The other subjects are in the standard risk group.

International Staging System (ISS) Stage at Baseline

ISS stage at baseline will be calculated using serum beta-2 microglobulin and serum albumin values collected at baseline, based on the criteria published by the International Myeloma Working Group (Greipp 2005):

[figure not shown]
Stage I: Serum beta-2 microglobulin < 3.5 mg/L and serum albumin ≥ 3.5 g/dL

Stage II:Serum beta-2 microglobulin < 3.5 mg/L and serum albumin < 3.5 g/dL or Serum beta-2 microglobulin 3.5–<5.5 mg/L irrespective of the serum albumin

Stage III: Serum beta-2 microglobulin ≥ 5.5 mg/L

Last Dose Date of Study Treatment

[figure not shown]
It is the latest date of drug taken among carfilzomib and dexamethasone.

Statistical Analysis Plan: 20140355

Date: 09 Jun 2017 Page 16

Overall Response Rate (ORR)

ORR is the proportion of subjects whose best overall response is PR, VGPR, CR, or sCR.

Overall Survival (OS)

OS time in months will be calculated from date of randomization until death due to any cause:

OS=(death date-randomization date +1)/30.4

Subjects still alive will be censored at the date last known to be alive. If the date last known to be alive is after the date that triggers the analysis, the subject will be censored at the analysis trigger date.

Progression-Free Survival (PFS)

PFS time will be calculated from the date of randomization until PD or death due to any cause, whichever occurs first:

PFS=(PD/death date-randomization date +1)/30.4

The duration of PFS will be right censored for subjects who meet 1 of the following conditions: 1) no baseline disease assessments; 2) starting a new anti-myeloma therapy before documentation of progressive disease or death; 3) progressive disease or death immediately after more than 1 consecutively missed disease assessment visit or; 4) alive without documentation of disease progression before the analysis trigger date. The

Statistical Analysis Plan: 20140355

Date: 09 Jun 2017 Page 17

censoring rules for PFS primary analysis are described in Table 1. These rules are based on the May 2007 FDA Guidance for Industry, 'Clinical Trial Endpoints for the Approval of Cancer Drugs and Biologics' (www.fda.gov/cder/guidance/7478fnl.htm).

Table 1. Censoring Rules for Primary PFS Analysis

Situation	Date of Progression or Censoring	Outcome
No baseline disease assessments	Date of randomization	Censored
New anti-myeloma treatment started before documentation of PD or death	Date of last disease assessment prior to start of a new anti-myeloma treatment	Censored
Death or PD immediately after more than 1 consecutively missed disease assessment visit*	Date of last disease assessment visit before the first missed visit	Censored
Alive and without PD documentation	Date of last disease assessment	Censored
Death or PD between planned disease assessments	Date of death or first disease assessment showing PD, whichever occurs first	Progressed
Death before first disease assessment	Date of death	Progressed

^{*} If death or PD is more than 64 days after previous disease assessment, or randomization date if there is no previous disease assessment..

Randomization Date

Randomization Date is defined as the date the subject was allocated to a treatment group. Per protocol, study treatment will ideally commence on the day of randomization, but at least within 5 calendar days of randomization.

Relative Dose Intensity (RDI)

RDI reflects whether the dose intensity of a therapy was implemented as planned. It will be calculated as the ratio of actual dose intensity relative to planned dose intensity.

Relative Dose Intensity (%) =
$$100 \times \frac{\text{Actual Dose Intensity}}{\text{Planned Dose Intensity}}$$

Carfilzomib: Actual dose intensity is defined as the actual amount of drug in mg/m² delivered to a subject per week of treatment.

Actual Dose Intensity
$$(mg/m^2/week) = \frac{\text{Cumulative Dose of Carfilzomib} (mg/m^2)}{\text{Number of Weeks of Actual Treatment}}$$

Statistical Analysis Plan: 20140355

Date: 09 Jun 2017 Page 18

Table 2. Planned Carfilzomib Dose per Week

Arm	Cycle	Week	Protocol Specified Dose for Treatment Week (mg/m2)
Once-weekly carfilzomib with dexamethasone	1	1 st	20
dexamethasone	2 or later	1 st	70
	All cycles	2 nd ,3 rd	70
	All cycles	4 th	0
Twice-weekly carfilzomib with	1	1 st	40
dexamethasone	2 or later	1 st	54
	All cycles	2 nd ,3 rd	54
	All cycles	4 th	0

Dexamethasone: Actual dose intensity is the actual amount of drug in mg delivered to a subject per week of treatment.

 $\label{eq:actual Dose Intensity (mg/week)} Actual \, Dose \, Intensity \, (mg/week) = \frac{Cumulative \, Dose \, of \, Dexamethasone \, (mg)}{Number \, of \, Weeks \, of \, Actual \, Treatment}$

CCI		

Statistical Analysis Plan: 20140355

Date: 09 Jun 2017 Page 19

Refractory to prior multiple myeloma therapy

Subject is refractory to a drug received in prior regimens if the data collected on prior multiple myeloma therapy CRF indicates that any of the following criteria is met:

- Best Response to any regimen containing the drug is stable disease or progressive disease
- b. Reason the drug was stopped is progression in any regimen
- c. Date of relapse/progression is after start date and within 60 days after stop date of the drug in any regimen

Study Day 1

Study day 1 is the earliest date when carfilzomib or dexamethasone is given for subjects who receive at least one dose of study drug, randomization date for subjects who are randomized but not treated.

Time to Response

Time to response will be calculated only for subjects who achieve a best overall response of PR or better, i.e., sCR, CR, VGPR, or PR. It will be calculated in months from randomization date to the earliest date a response of PR or better is first achieved and subsequently confirmed:

Time to Response=(response start date-randomization date +1)/30.4

Treatment-emergent Adverse Event

Statistical Analysis Plan: 20140355

Date: 09 Jun 2017 Page 20

AEs starting on or after first dose of investigational product as determined by the flag indicating if the adverse event started prior to the first dose on the Events CRF and up to and including 30 days after the end of study treatment.

7. Analysis Subsets

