10.1.3 COMPLETE PHYSICAL EXAMINATION

A physical examination will be performed during Screening, prior to dosing on Day 1 of each cycle, and at the EOT. For Cycle 1 Day 1, the screening physical examination may be used if performed within 7 days prior to Cycle 1 Day 1. Physical exam may be completed up to 3 days prior to Day 1 of each cycle. At a minimum, the physical exam should include constitutional, abdominal, cardiovascular, and respiratory assessments.

Clinically significant abnormal findings identified after the signing of informed consent must be reported as AEs and examined more frequently, as clinically indicated. Note: Clinically significant abnormal physical examination findings identified prior to the signing of informed consent should be reported as part of Medical History, not as AEs.

BSA is to be determined by a standard formula, such as the Mosteller Formula ([Mosteller 1987](#)): body surface area (BSA) (m²) = ([Height (cm) × Weight (kg)]/3600)^½. Body surface area must be recalculated and used for subsequent dose determinations, if the subject experiences a weight change of ≥ 20%. Recalculations of BSA must be made using the same technique as used at baseline.

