13.3 STATISTICAL METHODS

13.3.1 *ANALYSIS OF THE CONDUCT OF THE STUDY*

The number of subjects screened, randomized, and treated will be presented. The number and percentage of subjects excluded from each analysis population will be summarized with reasons for exclusion. The number of subjects who discontinue study treatment will be tabulated, along with the reason for discontinuation.

Subjects' demographics and baseline characteristics, disease characteristics, prior and concomitant medications, and study drug exposure and treatment compliance will be summarized descriptively for each treatment group.

The number and percentage of subjects with important protocol deviations will be summarized by treatment group.

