10.6.5 Exposure to Investigational Product

Descriptive statistics will be produced to describe the exposure to investigational product by treatment group for subjects in the Safety Analysis Set. The number of cycles of protocol-specified therapy administered will be summarized with an additional breakdown of the number of cycles started. In addition, the duration of therapy, the cumulative dose, and the average dose per administration and relative dose intenstiy will be summarized for each drug. The number and percent of subjects with dose modifications (eg, dose reductions, dose interruptions) and reason for modification will be summarized for both treatment groups.

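### The SAP updates the BSA divisor at a 20% change in BSA, but the protocol re-doses at a 20% change in weight, so mg/m² exposure and RDI are wrong for subjects between the two triggers

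*SAP*

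**What the plan says.** **Dosing.** Protocol Section 10.1.3 gives the Mosteller formula as an example and sets the rule for later doses: "Body surface area must be recalculated and used for subsequent dose determinations, if the subject experiences a weight change of" 20% or more.

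**Analysis.** SAP Section 6 (Cumulative Dose of Study Treatment) cites the same formula and divides each infusion's mg by a BSA chosen as follows: "The one collected on cycle 1 day 1 will be used in the calculation till when BSA changes ≥20% from cycle 1 day 1". After that, "Every time BSA changes ≥20% from current BSA used in the calculation, the new BSA will be used for subsequent infusions". It also limits the divisor: "If BSA is >2.2, then 2.2 will be used in the calculation".

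**Use.** In SAP Section 6 (Relative Dose Intensity), "RDI reflects whether the dose intensity of a therapy was implemented as planned", and for carfilzomib, "Actual dose intensity is defined as the actual amount of drug in mg/m² delivered to a subject per week of treatment". SAP Section 10.6.5 reports the results: "the cumulative dose, and the average dose per administration and relative dose intenstiy will be summarized for each drug". These outputs are descriptive. Protocol Section 13.3.1 says that "study drug exposure and treatment compliance will be summarized descriptively for each treatment group".

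SAP Section 11, which records departures from the protocol's analyses, lists only the change of test for ORR.

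**The concern.** The two rules share a threshold of 20% but apply it to different quantities. A subject whose weight passes the protocol threshold is dosed on a new BSA while the SAP still divides by the old one. The recorded mg/m² then differs from the mg/m² given, although the site did what the protocol asked.

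RDI is meant to show whether dose intensity was delivered as planned. Planned doses in SAP Table 2 are fixed mg/m² values, so the distortion enters through the numerator alone. Correct dosing after weight loss would look like under-dosing, and after weight gain like over-dosing. The trial compares two carfilzomib regimens, so delivered mg/m² and RDI are what a reader uses to judge whether each regimen was given as intended. Nothing in SAP Section 11 suggests that the different trigger was deliberate.

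**Working it through.** The plan states no figure for this mismatch, so there is none to reproduce.

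**Inputs**
- Dosing trigger: weight change of 20% or more (Protocol 10.1.3).
- Divisor trigger: BSA change of 20% or more (SAP Section 6).
- Mosteller: BSA = √(height in cm × weight in kg / 3600) (both documents).
- Doses after the step-up: 70 mg/m² once weekly and 27 mg/m² twice weekly (Protocol Figure 3). Weekly planned doses are from SAP Table 2.

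**Step 1: compare the triggers.** At fixed height, new BSA / old BSA = √(new weight / old weight).
- A 20% weight loss moves BSA by √0.80 − 1 = −10.6%. A 20% gain moves it by √1.20 − 1 = +9.5%.
- A 20% fall in BSA needs weight to change by 0.8² − 1 = −36%. A 20% rise needs 1.2² − 1 = +44%.

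**Step 2: error per infusion between the triggers.** Recorded / true mg/m² = dosing BSA / SAP divisor. With BSA not above 2.2 m²:

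| Weight change at re-dosing | Error | 70 mg/m² recorded as | 27 mg/m² recorded as |
|---|---|---|---|
| −20% | −10.6% | 62.6 | 24.1 |
| −30% | −16.3% | 58.6 | 22.6 |
| approaching −36% | just under −20% | just above 56.0 | just above 21.6 |
| +20% | +9.5% | 76.7 | 29.6 |
| +30% | +14.0% | 79.8 | 30.8 |
| approaching +44% | just under +20% | just below 84.0 | just below 32.4 |

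**Step 3: one illustrative subject.** Height 170 cm, weight falling from 80 to 64 kg.
- BSA goes from √(170 × 80 / 3600) = 1.944 to √(170 × 64 / 3600) = 1.739 m².
- Once weekly: 70 × 1.739 = 121.7 mg, recorded as 121.7 / 1.944 = 62.6 mg/m².
- Twice weekly: 27 × 1.739 = 46.9 mg, recorded as 46.9 / 1.944 = 24.1 mg/m².

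**Step 4: illustrative RDI.** Assume six full cycles, every planned dose given, the weight change just before Cycle 4, and the same weeks in actual and planned intensity.
- Once weekly: Cycle 1 is 20 + 70 + 70 = 160 and later cycles are 210 each, so the total is 160 + 5 × 210 = 1210 mg/m². Cycles 1 to 3 give 580 and Cycles 4 to 6 give 630.
- Twice weekly: Cycle 1 is 40 + 54 + 54 = 148 and later cycles are 162 each, so the total is 148 + 5 × 162 = 958 mg/m². Cycles 1 to 3 give 472 and Cycles 4 to 6 give 486.

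| Weight change | Once weekly | Twice weekly |
|---|---|---|
| −20% | (580 + 630 × 0.8944) / 1210 = 94.5% | (472 + 486 × 0.8944) / 958 = 94.6% |
| −30% | (580 + 630 × 0.8367) / 1210 = 91.5% | (472 + 486 × 0.8367) / 958 = 91.7% |
| +20% | (580 + 630 × 1.0954) / 1210 = 105.0% | (472 + 486 × 1.0954) / 958 = 104.8% |
| +30% | (580 + 630 × 1.1402) / 1210 = 107.3% | (472 + 486 × 1.1402) / 958 = 107.1% |

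Each should read 100%.

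**Step 5: effect on an arm mean.** The documents do not say how many subjects will change weight this much. Assume that 2% to 10% of an arm lose 20% and receive half their dose afterwards. The mean then shifts by 0.02 × 0.5 × −10.56 = −0.1% to 0.10 × 0.5 × −10.56 = −0.5%. Gains would offset this.

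**The case against.** **The consequence is small.** The affected outputs are descriptive, few subjects are likely to be involved, and the arm-mean shift is at most about half a percent on the assumptions used. This is true, and it limits the priority of the point. It does not make the individual values right.

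**The upper part of the range may seldom occur.** The protocol does not name the reference weight, and physical examinations take place every cycle. If change is measured from the last dosing weight and caught at exactly 20%, the next re-dosing falls at 0.8 × 0.8 = 0.64 or 1.2 × 1.2 = 1.44 of the starting weight, where the SAP also updates. The error then stays at −10.6% or +9.5%. Larger errors need either change measured from baseline with dosing on current weight, or a change well beyond 20% before recalculation. This stands: about 10% is the firm figure, and just under 20% is the limit.

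**The RDI figures rest on assumptions.** The readable SAP text gives neither the planned-intensity formula nor the definition of treatment weeks, and part of that section is redacted. The percentages in Step 4 are illustrations only.

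**Sites may recalculate earlier.** The protocol requires recalculation at 20% but does not forbid it sooner. If sites do so, errors also arise below 20%, and copying the weight trigger into the SAP would not remove them. Dividing by the BSA used for each dose would.

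**The 2.2 m² limit may be explained elsewhere.** The pharmacy instruction manual is not among the documents, so a dosing cap there cannot be excluded. That part is a query only.

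**Conclusion.** The concern holds. As written, the SAP gives a wrong mg/m², and hence a distorted carfilzomib RDI, for a subject re-dosed as the protocol requires. Under Mosteller, with BSA not above 2.2 m², the error per infusion between the triggers is −10.6% at a 20% loss and +9.5% at a 20% gain. It stays below 20% in either direction until the SAP divisor updates. Doses given before the weight change carry no error, provided that sites do not recalculate before 20%.

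The effect is confined to mg/m² cumulative dose, dose intensity, RDI and, if it is expressed in mg/m², average dose per administration. PFS, ORR, OS, mg totals and dose-modification counts are unaffected, and no bias between arms is shown. The number of subjects is unknown and probably small. This should be corrected before database lock, but it does not threaten the trial's conclusions.

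**What to change.** In SAP Section 6, divide each administered mg dose by the BSA used to calculate that dose. This brings the error to zero whatever the weight history. If that BSA was not recorded, update the divisor at the weight-change trigger in Protocol Section 10.1.3, and state the reference weight assumed.

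The preferred option has a drawback: it hides a site that failed to recalculate. After an unrecalculated 20% loss, the dose per current m² is 1/√0.8 − 1 = +11.8% from plan, and after a 20% gain it is 1/√1.2 − 1 = −8.7%, yet RDI would read 100%. Such infusions should be listed separately as deviations from Protocol Section 10.1.3.

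The 2.2 m² limit on the divisor should also be reconciled with the current protocol, which states no cap. No change to the dosing rule is proposed.

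The cost is a short edit to one definition, a programming change and one listing. Check before lock that the dosing BSA or later weights are in the database: the SAP mentions a BSA collected on Cycle 1 Day 1, but the assessment schedule in Protocol Appendix A does not list weight separately.
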